- ^a Patients will return to the clinic or will be contacted for a safety follow-up assessment 30 days \pm 3 days after the last dose of study drug was taken; or earlier if subsequent therapy for advanced malignancy is initiated prior to 30 days \pm 3 days.
- ^b Patients or their legally authorized representatives will be contacted every three months (\pm 7 days) until death, end of the study, or patient withdrawal of consent, whichever comes first. Survival and subsequent treatment status may be collected by public records, medical records, or by contacting the patient or their legally authorized representative by phone.
- ^c Full medical history at screening, only review/update of history at subsequent visits.
- ^d Oncologic history of the malignancy under study including prior regimens (duration of therapy, best response on therapy, date of discontinuation, and reason for discontinuation), surgery, and radiation therapy.
- ^e Physical examinations should be symptom driven after the Screening Visit.
- ^f Ophthalmological examinations will be performed by an ophthalmologist at screening, and whenever clinically indicated. In Part B, only patients in the ulixertinib arm need an ophthalmological exam. See section 10.1.5 for a full description of tests.
- ^g ONLY if the screening serum pregnancy test was performed more than 1 day previously.

- h After screening and baseline, if urine pregnancy test is positive, confirm with serum test.
- i Visit 2 clinical lab samples should be collected pre-dose if not done during Screening Visit within 72 hours of start of treatment.
- j Chemistry, hematology, and urinalysis. After Cycle 2, clinical labs to be performed prior to starting each new cycle or more frequently when clinically indicated at the investigator's discretion. See section 10.1.6 for a full description of test.
- k Patients with a normal ECG in Cycle 1 do not need to have repeat ECGs in subsequent cycles. Patients should be supine for 5 minutes prior to the ECG.
- l Tumor assessments will be made prior to dose initiation, at Visit 5, and then every 2 cycles. Patients who discontinue treatment for reasons other than progression will have assessments at the EOT visit (unless their previous assessment was performed within 28 days). The same imaging modality used for an individual patient (i.e. CT or MRI) at Screening should be maintained throughout the study.

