11.5.5.1 Part A

The primary endpoint for Part A is the overall response rate (ORR) within a group. It will be defined as the percentage of patients achieving a BOR of confirmed CR and/or PR as assessed by the investigator. The ORR will be presented with its 95% confidence intervals (CIs).

All response assessments will be presented using swimmer plots and will be listed by patient.

Sensitivity analyses of the primary analysis will include similar analyses using PP analysis set.

Analyses of secondary efficacy endpoints will include Kaplan-Meier estimates and curves, median DoR and respective 95% CIs for analysis of:

- Duration of response (DoR): time from first response to disease progression or death. Patients with no event will be censored at the last available tumor assessment. This analysis will be based on investigator assessment.
- Progression-free survival over 18 months (PFS): time from first day of trial medication to disease progression or death. Patients with no event will be censored at the last available tumor assessment. This analysis will be based on investigator assessment.
- Overall survival over 18 months (OS): time from first day of trial medication to death. Patients with no event will be censored at the last date the patient is known to be alive.

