### 9.8.3 Progression-free Survival (PFS)

The PFS (in months) is defined as the time from the first ulixertinib dose until the first radiographically documented progression of disease or death from any cause, whichever occurs first.

$$PFS = [(Date of first PD/death - Date of first study treatment) + 1] / 30.4375$$

Patients with no documented progression or death will be censored at the last available tumor assessment (last assessment that is CR, PR or SD):

$$PFS = [(Date of last assessment where patient is PD free - Date of first study treatment) + 1] / 30.4375$$

For patients with no post baseline tumor assessment a censored PFS at day 1 will be considered.

$$PFS = (Date of first study treatment - Date of first study treatment) + 1$$

The analysis of PFS will be performed with a Kaplan-Meier method (product-limit estimates) and a summary of associated statistics will be presented including corresponding two-sided 95% CI. The CI for the median will be calculated according to Brookmeyer and Crowley and CI for the survival function estimates at Month 3, 6, 9, 12, and 18 will be derived using the log-log transformation (SAS PROC LIFETEST CONFTYPE=LOGLOG). However, the final choice of timepoints may be updated dependent upon the data.

For Part B, for each histology, PFS curves will be compared between ulixertinib and physician's choice of treatment using Log Rank Test or other appropriate test if the proportional hazards assumption does not hold.

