**Statistical Analysis Plan:**

2.0 / 09-Jun-2023

BioMed Valley Discoveries  
Protocol: BVD-523-ABC ('Delivery' / 'Type') - Part X  
Data extraction date: DDMMYYYY

Page 1 of Y

Listing 16.2.6-5 - Duration of Response (DOR)  
Full Analysis Set

Group: Group 1

Subject ID	Age/ Gender	Best Overall Response [a]	Treatment Start Date	Date of First Response	Date of Last Tumor Assessment	Date of Event / Censoring	Event / Censoring Reason	Duration of Response (months)
xxx-xx	xx/M	CR	DDMMYYYY	DDMMYYYY	DDMMYYYY	DDMMYYYY	Death	xx.x
xxx-xx	xx/F	PR	DDMMYYYY	DDMMYYYY	DDMMYYYY	DDMMYYYY	Censored:xxxxx	xx.x

Note: M=Male, F=Female, CR=Complete Response, PR=Partial Response, SD=Stable Disease, PD=Progressive Disease, NE=Not Evaluable.

Event: progressive disease (PD) or death from any cause.

This listing includes only patients with response (CR or PR).

[a] Confirmed best overall response.

Program: (Program name.sas) (run on: DDMMYYYY HH:MM)

Filename: (Specify file name.rtf)

BioMed Valley Discoveries  
Protocol: BVD-523-ABC ('Delivery' / 'Type') - Part X  
Data extraction date: DDMMYYYY

Page 1 of Y

Listing 16.2.6-6 - Progression-Free Survival (PFS)  
Full Analysis Set

Group: Group 1

Subject ID	Age/ Gender	Treatment Start Date	Date of Last Tumor Assessment	Date of Event/ Censoring	Event / Censoring Reason	PFS (months)
xxx-xx	xx/M	DDMMYYYY	DDMMYYYY	DDMMYYYY	Death	xx.x
xxx-xx	xx/F	DDMMYYYY	DDMMYYYY	DDMMYYYY	Censored: xxxxx	xx.x

Note: M=Male, F=Female, PFS=Progression-Free Survival.

Event: progressive disease (PD) or death from any cause.

The PFS (in months) is defined as the time from the first ulixertinib dose until the first radiographically documented progression of disease or death from any cause, whichever occurs first.

Program: (Program name.sas) (run on: DDMMYYYY HH:MM)

Filename: (Specify file name.rtf)

**Sponsor:** BioMed Valley Discoveries

**Protocol:** BVD-523-ABC

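### The day-1 censoring sentence in SAP 9.8.3 does not exempt patients who die before their first scan, so it conflicts with the section's own definition of a PFS event

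*SAP*

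**What the plan says.** SAP 9.8.3 sets out PFS in three steps, each with its own formula.

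1. Event. PFS runs from first dose "until the first radiographically documented progression of disease or death from any cause, whichever occurs first". The formula uses the date of first progression or death, and no scan is required before a death counts.
2. Censoring with a scan available. "Patients with no documented progression or death will be censored at the last available tumor assessment".
3. Censoring with no scan available. "For patients with no post baseline tumor assessment a censored PFS at day 1 will be considered". The accompanying formula is the first-dose date minus itself, plus 1, without the division by 30.4375 used in the other two.

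Protocol 11.5.5.1 defines PFS as "time from first day of trial medication to disease progression or death" and gives one censoring rule: "Patients with no event will be censored at the last available tumor assessment". Protocol 11.5.5.2 applies the same rule in Part B. The protocol has no day-1 rule, and SAP section 11 does not list one among the changes to planned analyses.

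On timing, footnote l of protocol Table 3.1 says: "Tumor assessments will be made prior to dose initiation, at Visit 5, and then every 2 cycles". Visit 5 is Day 29 ± 3.

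**The concern.** Step 2 states whom it applies to: patients with neither progression nor death. Step 3 does not repeat that condition. Read alone, it takes in everyone without a post-baseline scan, including those who died before one could be done.

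Such deaths are foreseeable. Patients have locally advanced or metastatic disease, mostly after earlier systemic therapy, with ECOG 0 to 2, and the first scan comes about four weeks after the first dose. SAP 9.8.1 anticipates the problem for ORR: it keeps in the denominator patients who have no post-baseline measurement for reasons attributable to progression. The PFS section has no matching safeguard.

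If the earliest failures are censored at day 1, they leave the risk set before any event is counted and later PFS estimates rise. Outputs would also disagree: the same death would be an event for OS and would end the patient's bar in the swimmer plot, yet be a day-1 censoring in the PFS table. Table 14.2-1.5.1, Figure 14.2-1.6.1 and Listing 16.2.6-6 are all marked for the final analysis.

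**Working it through.** No figure in the plan depends on this rule, so there is none to reproduce. The check is a trace of one patient through the text, then the size of the effect if the sentence is coded literally.

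**One patient under each rule.** Suppose a patient dies on Day 20 with no post-baseline scan.
- Event rule: PFS = 20/30.4375 = 0.66 month, event.
- Day-1 rule: censored at day 1, which is 1/30.4375 = 0.033 month.

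Both conditions are met and the text does not rank them.

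**Inputs.** Group size is 38 (SAP 6.4, Part A target). The fraction d who die without a scan is not in the documents; it is assumed to lie between 3% and 20%. No PFS assumption is given for Part A. The Part B planning medians, 1.7 to 8.5 months on physician's choice and twice that on ulixertinib (3.4 to 17), are borrowed for scale.

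**Effect on PFS rates.** Censoring at day 1 removes these patients from the risk set, so after the first scan S_literal(t) = S(t)/(1−d).
- 3 deaths: d = 3/38 = 0.079; 0.50 × 38/35 = 0.543.
- 5 deaths: d = 5/38 = 0.132; 0.50 × 38/33 = 0.576.

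**Effect on the median, early deaths added to an exponential group.** If the remaining patients have an exponential median of 3.0 months, the literal rule reports 3.0. The true median solves 2^(−t/3) = 0.5/(1−d), giving t = 2.64 months with 3 deaths and 2.39 months with 5.

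**Effect on the median, whole group exponential.** Here median_literal = median × [1 + log2(1/(1−d))].

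| d | PFS rates × | median × | 3.4-month median becomes |
|---|---|---|---|
| 3% | 1.03 | 1.04 | 3.55 |
| 5% | 1.05 | 1.07 | 3.65 |
| 10% | 1.11 | 1.15 | 3.92 |
| 20% | 1.25 | 1.32 | 4.49 |

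The range has a ceiling, because d cannot exceed the share of all PFS events occurring by about day 32. For exponential PFS that share is 1 − 2^(−(32/30.4375)/median): about 35%, 19%, 8% and 4% for medians of 1.7, 3.4, 8.5 and 17 months. The 20% row is therefore reachable only when the median is very short.

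**Product-limit check.** Take 38 event times at the quantiles of an exponential with median 3.4 months, and treat the 4 earliest (0.06 to 0.47 month) as unscanned deaths.

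| | Deaths as events | Censored at day 1 |
|---|---|---|
| KM median (months) | 3.27 | 3.80 |
| 3-month PFS | 21/38 = 55.3% | 21/34 = 61.8% |
| 6-month PFS | 11/38 = 28.9% | 11/34 = 32.4% |

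Both rates rise by 38/34 = 1.118, as the formula predicts.

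**Units.** The day-1 formula returns 1 on a variable defined in months. Taken literally it censors at 1 month, not 0.033 month. In the same example, censoring the 4 deaths at 1 month moves the median further, to 4.09 months.

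**The case against.** The strongest reply is that the sentence should be read in its place. The section has already made death an event, and the sentence just before limits censoring to patients without progression or death. That rule needs a last assessment date, and the day-1 sentence supplies a date when there is none. On this reading a Day 20 death never reaches the censoring rules and the bias is zero.

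The surrounding text supports this. The protocol censors only patients without an event. The footnote to the Listing 16.2.6-6 shell reads "Event: progressive disease (PD) or death from any cause", and the shell shows a death as an example event. The swimmer-plot shell ends the PFS bar at progression or death. SAP section 11 expects no major change from the protocol.

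Other points also limit the stakes. A wrongly censored death could be caught by comparing the PFS, survival-status and deaths listings. The exposed group is smaller than all deaths before Day 29, since patients who stop early are due an end-of-treatment assessment and unscheduled assessments count in time-to-event analyses (SAP 7.7 and 7.8). Part A PFS is secondary and has no hypothesis test. The group size of 38 is a target set before early termination.

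All of this stands. A reader might infer from the day-1 sentence alone that the SAP discards early deaths and that reported PFS will be overstated; the documents taken together do not support that. What the reply does not remove is the conflict in the text. No passage gives death precedence over the day-1 rule, and the shells define the event without addressing the unscanned case.

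**Conclusion.** The day-1 sentence is wrong as written: it conflicts with the event definition in its own section and with the protocol's censoring rule. Whether it biases anything depends on how it is programmed. Read as a sub-case of the preceding rule, it does no harm. Coded literally, it inflates later Kaplan-Meier PFS by 1/(1−d), always upward; for 3 to 5 unscanned deaths in 38, a 50% rate becomes 54.3% to 57.6%. Those counts are assumptions, and the median shifts also assume exponential PFS.

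The effect is confined to descriptive secondary reporting in Part A; ORR, the primary endpoint, is untouched. A reader might extend the point to a biased primary comparison in Part B. That does not follow from this plan: SAP 7.2 records termination during Part A and leaves the Part B analysis to a later version. Bias there would require Part B to be run, the sentence to be carried over and coded literally, and early unscanned deaths to differ between arms.

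The correction is worth making because the PFS outputs are still to be delivered, but its severity is below must-fix.

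**What to change.** Replace the sentence in SAP 9.8.3 with: *Patients with no post-baseline tumor assessment who have not died are censored at day 1; a patient who dies without a post-baseline tumor assessment has a PFS event on the date of death.*

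Apply this in the PFS programs and in Listing 16.2.6-6, and carry it into any later Part B version of the SAP. Divide the day-1 formula by 30.4375 so that it gives 0.033 month.

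The cost is one clause, one divisor and a line of code for each. No new data are needed, and the change restores the SAP's own definition and the protocol's rule.

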**Study day**

Study day will be calculated as (assessment date – date of first study treatment dose) for pre-baseline assessments and [(assessment date – date of first study treatment dose) + 1] for post-baseline assessments, i.e. there will be no study day 0 and study day 1 will correspond to the first study treatment dose.

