#### 9.8.2 Duration of Response (DOR)

The duration of response (in months) is defined as the period from the date of initial confirmed PR or CR until the date of first radiographically documented progressive disease or death from any cause. Only patients with BOR of CR or PR (i.e. responders) will be included in the analysis of duration of response.

$$DOR = [(Date of first PD/death - Date of first recorded confirmed CR/PR) + 1] / 30.4375$$

Patients with no documented progression or death after CR or PR will be censored at the last available tumor assessment (last assessment that is CR, PR, or SD):

$$DOR = [(Date of last assessment - Date of first recorded CR/PR) + 1] / 30.4375$$

The analysis of DOR will be performed with a Kaplan-Meier method (product-limit estimates) and a summary of associated statistics will be presented including corresponding two-sided 95% CI. The CI for the median will be calculated according to Brookmeyer and Crowley and CI for the survival function estimates at Month 3, 6, 9, 12, and 18 will be derived using the log-log transformation (SAS PROC LIFETEST CONFTYPE=LOGLOG), only if there are sufficient data for responders. However, the final choice of timepoints may be updated dependent upon the data.

Part B, DOR will be compared between ulixertinib and physician's choice of treatment using a Log Rank test or other appropriate test if the proportional hazards assumption does not hold.

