### 9.8.4 Overall Survival (OS)

The OS (in months) is defined as the time from first treatment to death. Patients who did not die during the study will be censored at the last known alive date.

$$OS = [(Date of death - Date of first study treatment) + 1] / 30.4375$$

For censored patients:

$$OS = [(Last known alive date - Date of first study treatment) + 1] / 30.4375$$

The last known alive date will be determined among study treatment administrations, any visits where at least one assessment has been completed, or any follow-up assessment where the patient has been confirmed to be alive.

OS will be analyzed using the same Kaplan-Meier method used to analyze the DOR.

Part B, OS will be compared between ulixertinib and physician's choice of treatment using a Log Rank Test or other appropriate test if the proportional hazards assumption does not hold.

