**PROGRAMMING NOTES:**

- Repeat Table 14.2-1.4.1
- Present data on Evaluable Analysis Set.

Table 14.2-1.5.1 - Progression-Free Survival (PFS)  
Full Analysis Set

	Group 1 N=XX	Group 2 N=XX	Group 3 N=XX	Group 4 N=XX	Group 5 N=XX	Group 6 N=XX	Overall N=XX
Patients with events - n (%)	XX (XX.X)	XX (XX.X)	XX (XX.X)	XX (XX.X)	XX (XX.X)	XX (XX.X)	XX (XX.X)
Patients censored - n (%)	XX (XX.X)	XX (XX.X)	XX (XX.X)	XX (XX.X)	XX (XX.X)	XX (XX.X)	XX (XX.X)
PFS (months) [a]							
Median (95% CI)	XX (X.X, X.X) (X.X, X.X)	XX (X.X, X.X)	XX (X.X, X.X)	XX (X.X, X.X)	XX (X.X, X.X)	XX (X.X, X.X)	XX (X.X, X.X)
Min, Max	XX, XX* XX, XX	XX, XX	XX, XX	XX, XX* XX, XX	XX, XX	XX, XX* XX, XX	XX, XX
KM probability estimates for PFS (95% CI) [b]							
3 Months	XX (X.X, X.X)	XX (X.X, X.X)	XX (X.X, X.X)	XX (X.X, X.X)	XX (X.X, X.X)	XX (X.X, X.X)	XX (X.X, X.X)
6 Months	XX (X.X, X.X)	XX (X.X, X.X)	XX (X.X, X.X)	XX (X.X, X.X)	XX (X.X, X.X)	XX (X.X, X.X)	XX (X.X, X.X)
9 Months	XX (X.X, X.X)	XX (X.X, X.X)	XX (X.X, X.X)	XX (X.X, X.X)	XX (X.X, X.X)	XX (X.X, X.X)	XX (X.X, X.X)
12 Months	XX (X.X, X.X)	XX (X.X, X.X)	XX (X.X, X.X)	XX (X.X, X.X)	XX (X.X, X.X)	XX (X.X, X.X)	XX (X.X, X.X)
18 Months	XX (X.X, X.X)	XX (X.X, X.X)	XX (X.X, X.X)	XX (X.X, X.X)	XX (X.X, X.X)	XX (X.X, X.X)	XX (X.X, X.X)

Note: CI=Confidence Interval.

Progression-Free Survival (PFS) is the time from the first ulixertinibdose until the first radiographically documented progression of disease or death from any cause, whichever occurs first.

[a] Product-limit (Kaplan-Meier) estimates. 95% CI for median calculated using the Brookmeyer and Crowley method.

[b] Based upon Kaplan-Meier (KM) estimates and 95% CI use the log-log transformation.

\* Censored observation at maximum value.

Program: (Program name.sas) (run on: DDMMYYYY HH:MM)

Filename: (Specify file name.rtf)

**Sponsor:** BioMed Valley Discoveries

**Protocol:** BVD-523-ABC

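### SAP 9.8.3: the PFS formula for patients with no post-baseline scan omits the division by 30.4375, so coded as printed it censors them at 1.0 month instead of day 1 (0.033 month)

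*SAP*

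**What the plan says.** SAP section 9.8.3 sets the unit at the start: "The PFS (in months) is defined as the time from the first ulixertinib dose". The event formula follows it: "PFS = [(Date of first PD/death - Date of first study treatment) + 1] / 30.4375". The formula for patients censored at their last progression-free scan uses the same divisor.

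Patients who were never scanned after baseline get a separate rule: "For patients with no post baseline tumor assessment a censored PFS at day 1 will be considered". The formula printed beneath is "PFS = (Date of first study treatment - Date of first study treatment) + 1", with neither the outer square brackets nor the divisor.

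The neighbouring sections convert to months throughout. In 9.8.2 the censored duration is "DOR = [(Date of last assessment - Date of first recorded CR/PR) + 1] / 30.4375", and in 9.8.4 censored survival is "OS = [(Last known alive date - Date of first study treatment) + 1] / 30.4375". The event formulas for DOR and OS have the same form.

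The shells present PFS in months in Table 14.2-1.5.1, Figure 14.2-1.6.1 and Listing 16.2.6-6. None of them carries a footnote or programming note that converts the value for never-scanned patients. All three are marked for inclusion in the final analysis on the Full Analysis Set.

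**The concern.** The sentence and the formula for never-scanned patients give different times once the result is placed in the months variable that the section defines. The sentence means the day of first dose. The formula gives 1, which on that scale is a full month.

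The difference matters because of where the first scan falls. Protocol section 10.3.2.1 places Visit 5 at Day 29 ± 3, and footnote l of Table 3.1 puts the first on-treatment tumor assessment there. One month is 30.4 days, inside that window. A patient censored on day 1 contributes nothing to the risk set at the first scan. A patient censored at 1.0 month is still counted at risk when most of that window's progressions are recorded, without ever having been examined for progression. The denominator is then too large and the estimated drop too small.

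The group need not be empty: SAP 9.8.1 provides for patients with no post-baseline efficacy measurement.

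**Working it through.** **Inputs.** The unit (months), the divisor 30.4375 and the never-scanned formula come from SAP 9.8.3. The first scan at Day 29 ± 3, with later scans every two 28-day cycles, comes from Protocol 10.3.2.1 and Table 3.1. The second scan is therefore on Day 29 + 56 = 85. The planned group size of 38 comes from SAP 6.4.

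**Step 1: the formula as printed.** With d the date of first dose, (d − d) + 1 = 1. Read in days this reproduces the plan's day 1 and agrees with the study-day convention in SAP 7.8, under which "there will be no study day 0 and study day 1 will correspond to the first study treatment dose".

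**Step 2: the same quantity in months.** [(d − d) + 1] / 30.4375 = 1 / 30.4375 = 0.033 month. Entering the printed 1 in the months variable gives a value too large by a factor of 30.4375. Listing 16.2.6-6 shows one decimal, so such a patient would print as 1.0 instead of 0.0.

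**Step 3: the first-scan window in months.**

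| Study day | Months | Before 1.0 month? |
|---|---|---|
| 26 | 26/30.4375 = 0.854 | yes |
| 29 | 29/30.4375 = 0.953 | yes |
| 30 | 30/30.4375 = 0.986 | yes |
| 31 | 31/30.4375 = 1.018 | no |
| 32 | 32/30.4375 = 1.051 | no |

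Events up to Day 30 are divided by a risk set that wrongly includes the never-scanned patients. From Day 31 the two risk sets are identical.

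**Step 4: effect on the curve (illustration only).** The documents give neither the number of never-scanned patients nor the achieved group sizes, so the counts below are assumed. Take N patients, u = 2 never scanned, d1 progressions on Day 29 and d2 on Day 85 (2.793 months), with no other events or censoring before Month 3 (91.3 days), which is a planned row of the table.

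- Literal: (1 − d1/N) × (1 − d2/(N − u − d1))
- Corrected: (1 − d1/(N − u)) × (1 − d2/(N − u − d1))

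| N, d1, d2 | Literal | Corrected | Difference (points) |
|---|---|---|---|
| 38, 10, 6 | (28/38)(20/26) = 0.567 | (26/36)(20/26) = 0.556 | +1.1 |
| 38, 15, 5 | (23/38)(16/21) = 0.461 | (21/36)(16/21) = 0.444 | +1.7 |
| 20, 5, 3 | (15/20)(10/13) = 0.577 | (13/18)(10/13) = 0.556 | +2.1 |

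If the d1 progressions fall on Day 31 or 32 instead, the difference is 0 in every row. After Day 30 the two curves differ by a constant ratio: 1.020, 1.038 and 1.038 in these three cases.

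**The case against.** The best defence is that the intent is plain. The formula returns a bare 1, and the sentence directly above supplies the unit, day 1. Only a programmer who ignored that sentence would store 1.0 month. An error would also be easy to see, because Listing 16.2.6-6 prints the treatment start date, the censoring date and PFS side by side, and two equal dates beside 1.0 would stand out.

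The consequence also needs several things together: literal coding, at least one treated patient with neither a post-baseline scan nor a death, and events by Day 30. SAP 9.8.1 is thin evidence for such patients. It concerns measurements missing for reasons attributable to progression, and any of those patients who died are PFS events, not censored. The trial stopped during Part A (SAP 7.2), so Part B, where PFS would have been primary and tested, is not being analysed. The report is abbreviated and centred on safety.

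All of this limits the weight of the point, and it is why the curve figures are offered only as illustrations. It does not make the formula right. Following the formula contradicts the sentence, and following the sentence departs from the formula. The clear intent only makes the correction uncontroversial.

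**Conclusion.** The formula is wrong as written for a variable in months. It gives 1.0 where the section's own rule requires 0.033. That much follows from the documents alone.

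Whether any reported result is affected depends on how the program was written and on how many patients reach this rule, and the documents show neither. If the literal formula was used, the bias in early PFS is zero or upward. It was 0 to 2.1 percentage points at Month 3 under the assumed counts, and each affected patient's listed value is wrong. This is a minor correction to a descriptive secondary endpoint. It is worth making because the rule feeds outputs that are still to be delivered. ORR, DOR and OS do not use this formula.

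**What to change.** With d the date of first study treatment, write the never-scanned formula as PFS = [(d − d) + 1] / 30.4375, matching the other six. Then check the PFS program: in Listing 16.2.6-6, any patient censored on the treatment start date should show 0.0, not 1.0.

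As a secondary clarification, limit the day-1 censoring sentence to patients with neither a post-baseline assessment nor a death. The PFS definition already counts death from any cause as an event, so this changes no rule; it only removes a possible misreading.

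The cost is one formula, a few words and one program check. The FAS PFS table, figure and listing need rerunning only if the program followed the printed formula.

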11.2.2 Part B

It is not possible to accurately calculate the required sample size until the histologies of interest have been confirmed. Once the histologies of interest have been confirmed these calculations will be repeated and the final sample size confirmed.

Approximately 80-100 patients will be randomized, using a 2:1 ratio, for each histology group in Part B.

Using a 2-sided, log-rank test with a 5% alpha, and assuming a median PFS of 1.7 to 8.5 months (depending on histology) in the physician's choice arm and twice as long on the ulixertinib arm, approximately 80 to 100 patients will be required in each group to achieve 80% power to show a statistically significant difference between the arms. This also assumes that each group will take approximately 24 months to accrue and the analysis is expected to be performed 18 months following the last patient accrued. The anticipated loss to follow-up is estimated to be 10%.

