11.5.5.2 Part B

The primary endpoint for Part B is the Progression-Free Survival over 18 months (PFS), defined as time from first day of trial medication to disease progression as adjudicated by the independent review committee or death. Patients with no event will be censored at the last available tumor assessment. PFS will be analyzed using Kaplan-Meier estimates and curves, median PFS and respective 95% CIs.

For each histology, PFS curves will be compared between ulixertinib and physician's choice of treatment using Log Rank Test. The hazard ratio including 95% CI will be calculated by Cox's Proportional Hazards model.

Sensitivity analyses of the primary analysis will include similar analyses based on investigator response assessment and using PP analysis set.

Analyses of secondary efficacy endpoints will include analyses similar to PFS analysis for:

- Overall survival over 18 months (OS): time from first day of trial medication to death. Patients with no event will be censored at the last date the patient is known to be alive.
- Duration of response (DoR): time from first response to disease progression or death. Patients with no event will be censored at the last available tumor assessment. This analysis will be based on assessment as adjudicated by the independent review committee and replicated on investigator assessment.
- Overall response rate (ORR), defined as the percentage of patients achieving a BOR of confirmed CR and/or PR, will be presented with its 95% CIs and compared between ulixertinib and physician's choice of treatment using a Chi-square test. This analysis will be based on assessment as adjudicated by the independent review committee and replicated on investigator assessment.

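### SAP 9.8.3 lets an unnamed test replace the Part B primary log-rank test after a proportional-hazards check: the switch is unnecessary, undeclared, and modestly raises the type I error

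*SAP*

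**What the plan says.** PFS is the Part B primary endpoint. For each histology, SAP 9.8.3 compares the two arms "using Log Rank Test or other appropriate test if the proportional hazards assumption does not hold". It does not say how proportional hazards (PH) will be assessed, at what level it fails, which test then applies, or how alpha is handled. The same rule covers the two secondary time-to-event endpoints: overall survival in SAP 9.8.4 ("Log Rank Test or other appropriate test if the proportional hazards assumption does not hold") and duration of response in SAP 9.8.2 ("Log Rank test or other appropriate test if the proportional hazards assumption does not hold").

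The protocol has no such branch. Section 11.5.5.2 compares ulixertinib with physician's "choice of treatment using Log Rank Test", plus a Cox hazard ratio with its 95% interval, and the synopsis also names only the log-rank test. Protocol 11.2.2 sizes Part B on a two-sided 5% log-rank test with median PFS "twice as long on the ulixertinib arm" and enough patients "to achieve 80% power to show a statistically significant difference between the arms". SAP 6.4 repeats that calculation.

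SAP section 11 expects no major change from the protocol's analyses. It lists a new analysis population and a reduced set of demographic tables, but not this change of test.

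**The concern.** Whether PH holds can be judged only from the trial's own data by arm. Under SAP 9.8.3 the primary test is therefore settled after the comparative data are seen, by a criterion and a menu that nobody has written down.

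The usual reason for such a clause is that the log-rank test needs PH to be valid. It does not. If the two survival curves are equal, the hazards are equal throughout and the log-rank test has its nominal level. Non-proportional hazards reduce its power and complicate the reading of a single hazard ratio; they do not create false positives.

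At stake are the meaning of the stated 5% level for the primary endpoint, the match between the power statement and the test actually used, and the ease with which a positive result could be challenged.

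**Working it through.** **1. Does the planned sample size belong to the log-rank test?**

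Inputs from Protocol 11.2.2: two-sided alpha 5%, power 80%, 2:1 allocation, control median 1.7 to 8.5 months, median doubled on ulixertinib (hazard ratio 0.5 if PFS is exponential), 24 months' accrual, 18 months' further follow-up, 10% loss.

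Events (Schoenfeld): D = (1.960 + 0.842)² / [(2/3)(1/3)(ln 0.5)²] = 7.85 / (0.2222 × 0.4805) = 73.5, so 74.

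Event probability per arm, with uniform accrual and λ = ln 2 / median: 1 − (e^(−18λ) − e^(−42λ)) / (24λ).

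- Control median 8.5: 0.899 (control) and 0.694 (ulixertinib). Averaged 1:2, (0.899 + 2 × 0.694)/3 = 0.762.
- Control median 1.7: the same average is 0.997.

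| Control median | N without loss | N with exponential loss, 10% over 42 months | N divided by 0.90 |
|---|---|---|---|
| 1.7 months | 74/0.997, so 75 | 76 | 84 |
| 8.5 months | 74/0.762, so 98 | 100 | 109 |

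The planned 80 to 100 per histology is reproduced as a log-rank calculation. The 80% power statement does not carry over to an unnamed substitute.

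**2. What does the two-step rule do to the type I error?**

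The documents give neither the check nor the alternatives, so these are assumptions:

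- PH check: Schoenfeld-residual trend test at 5%, 10% or 20%.
- Alternatives: Gehan, Peto (Fleming-Harrington (1,0)), FH(0,1) and FH(1,1).

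With the usual normal critical value, the log-rank test alone rejects in 5.7% (N=82) and 5.2% (N=100) of null trials. To keep this small-sample effect out of the comparison, each test's critical value was set so that it rejects in exactly 5% of null trials when used alone. Both arms have the same PFS distribution, with 40,000 trials per scenario. The Monte Carlo standard error is about √(0.05 × 0.95/40,000) = 0.1 percentage point.

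Rejection rate (%) when log-rank is used unless the PH check fails:

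| Scenario | PH check level | Gehan | Peto | FH(0,1) | FH(1,1) | Best of four |
|---|---|---|---|---|---|---|
| N=82, median 1.7 | 5% | 5.45 | 5.44 | 5.86 | 5.14 | 6.52 |
| | 10% | 5.62 | 5.60 | 6.22 | 5.20 | 7.27 |
| | 20% | 5.78 | 5.77 | 6.47 | 5.22 | 8.20 |
| N=100, median 8.5 | 5% | 5.42 | 5.36 | 5.83 | 5.13 | 6.52 |
| | 10% | 5.69 | 5.62 | 6.14 | 5.18 | 7.34 |
| | 20% | 5.90 | 5.82 | 6.42 | 5.28 | 8.40 |

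A separate run of 20,000 trials per scenario gave 5.1-6.6% for one replacement and 6.5-8.4% for the best of four.

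**3. Why it rises.** Under the null, the log-rank statistic is roughly independent of the PH check, whereas a test that weights early or late events is correlated with it. Take N=100, a 10% check and FH(0,1). The rule's error is about 0.90 × 5.0% + 0.10 × r = 6.14%, so r = (6.14 − 4.50)/0.10 = 16.4%. Among null trials that fail the check, the replacement rejects about one in six.

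**4. With log-rank fixed as the only primary test,** the calibrated error is 5.0%, and 74 events and 80 to 100 patients stand unchanged.

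**The case against.** The strongest reply is that this analysis will not be run. SAP 7.2 records that the study stopped during Part A and that an abbreviated, safety-focused report will follow. SAP section 4 and 7.2 also leave further Part B detail to a later version, which could have named the check and the test before any Part B data existed. Both statements are correct, and they limit the consequence. They do not correct the sentence: this SAP says that it covers both parts, and nothing in it says that the clause would be withdrawn.

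Second, the inflation is small. With one alternative fixed in advance it runs from about 0.1 to 1.6 points, and the low end can hardly be told from 5%. That stands. A reader might infer that the clause destroys control at 5%, or that it licenses picking the smallest p-value. The documents support neither: the wording refers to one other test, conditional on failed PH, and the 6.5-8.4% range needs an analyst to go beyond it.

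Third, the sizes depend on checks and alternatives that the documents do not give. That also stands, and it is why ranges are shown.

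Fourth, Protocol 11.1 calls its statistical section a summary, and 11.7 allows analysis changes if they are documented in a SAP change log and the study report. So changing the test is not in itself improper. What remains is that SAP section 11 does not declare it.

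Finally, the alpha argument concerns the primary test. It does not carry over to overall survival or to duration of response, which covers responders only; there the case is agreement with the protocol.

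**Conclusion.** The point holds, at modest size. The SAP adds an undefined, data-dependent replacement for the Part B primary test. The protocol and the sample-size basis do not contain it, SAP section 11 does not declare it, and validity does not require it. The type I error becomes about 5.1-6.6% with one replacement fixed in advance, and about 6.5-8.4% only if the most favourable of four is chosen. These figures rest on an assumed Schoenfeld-type check at 5% to 20%, four assumed weighted log-rank alternatives, and the two ends of the control-median range in Protocol 11.2.2.

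A reader might infer that a trial result is compromised. The documents do not support that: the study ended during Part A, so no reported Part A result is affected. The point applies to the Part B plan as it stands in SAP 2.0 and to any reuse of its text. It is worth correcting because the correction is nearly free.

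**What to change.** In SAP 9.8.3, end the sentence at the log-rank test and delete the clause that allows another test when PH fails. Then state: the two-sided log-rank test is the primary PFS test in each histology, whatever the PH assessment shows; one named method, for example restricted mean survival time to a pre-stated time point, is always reported as a sensitivity analysis. Reporting it in every case removes the need for a trigger. The time point must be fixed before Part B data are seen; the documents give none.

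Make the same deletion in SAP 9.8.2 and 9.8.4 for consistency with the protocol. If a different primary test is in fact wanted, name it, re-derive the sample size for it, and declare the change in SAP section 11.

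The cost is about one sentence per section, and the sample size does not change. The downside is possible loss of power if hazards prove non-proportional, a case that the documents do not discuss.
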